9.6 Dietary or Other Protocol Restrictions

There are no dietary or other protocol restrictions for this study. Alcohol should be avoided starting at the time of informed consent for study participation and for the first 52 weeks of the study, and particularly within 48 hours prior to lab work. Alcohol use should be minimized throughout the remaining duration of the study.

Subjects should be advised to abstain from any blood or sperm donation after BMN 270 infusion, until there is no further evidence of vector shedding from PCR analysis of blood and semen samples, respectively. Subjects should also abstain from organ donation.

9.7 Safety and Efficacy Variables

9.7.1 Safety and Efficacy Measurements Assessed

The Schedule of Events ([Table 9.1.1](#) through [Table 9.1.4](#)) describes the timing of required evaluations.

9.7.2 Primary Efficacy Variables

9.7.2.1 FVIII Activity

The primary efficacy variable is change of the hFVIII activity, as measured by chromogenic substrate assay during Weeks 49-52 post-BMN 270 infusion from baseline.

If a subject has used FVIII within 72 hours of a measurement day, all efforts should be made to obtain FVIII activity measurements when a 72-hour interval without FVIII use is achieved; The 72-hour wash-out period is only intended for subjects who have achieved $FVIII \geq 5 \text{ IU/dL}$ at the end of 16 weeks after BMN 270 infusion and who have not resumed FVIII replacement therapy.

Note that fluctuations in FVIII activity after gene therapy are common, and more frequent monitoring of FVIII activity levels is not needed in the absence of a concurrent or recent ALT elevation or upon consultation between the Investigator and the Medical Monitor.

Details on collecting FVIII activity samples are included in the Laboratory Manual.

9.7.3 Secondary Efficacy Variables

9.7.3.1 Factor VIII Replacement Therapy/Bleeding Episodes

Secondary efficacy variables include:

- Change in the annualized utilization (IU/kg/year) and infusion (number/year) rates of exogenous FVIII replacement therapy from Week 5 post-BMN 270 infusion to last visit by data cutoff (for Week 52 analysis) from the baseline number and utilization of exogenous FVIII replacement therapy for subjects receiving FVIII prophylaxis during the 12 months prior to study entry, or change in administration of exogenous FVIII replacement therapy from Week 27 post-BMN 270 infusion to last visit by data cutoff (for Week 52 analysis) for subjects receiving prior emicizumab prophylaxis.
- Change in the annualized number of bleeding episodes requiring exogenous FVIII replacement treatment (annualized bleeding rate, ABR) from Week 5 post-BMN 270 infusion to last visit by data cutoff (for Week 52 analysis) for subjects receiving prior FVIII prophylaxis, or from Week 27 post-BMN 270 infusion to last visit by data cutoff (for Week 52 analysis) for subjects receiving prior emicizumab prophylaxis, compared to the baseline ABR during the 12 months prior to study entry.

Subjects must have high quality documented historical data available concerning previous bleeding episodes and hemophilia treatment over the previous 12 months in order to be eligible to enroll in the study. During the study, subjects will be asked at each study visit to report the use of factor replacement therapy and the number of bleeding episodes since the previous visit. This information will be captured on the subject's diary or other subject records. Subjects will be encouraged to discuss any bleeding episodes with the Investigator and attempt to objectively assess any reported bleeds through use of ultrasound or non-invasive imaging.

Subjects are strongly encouraged to immediately consult Investigator for guidance regarding exogenous FVIII administration for suspected bleeds or bleeding episodes within the first 30 days post-BMN 270 infusion.

In subjects who experience recurrent bleeding episodes, the Investigator and Medical Monitor will discuss whether to resume prior FVIII prophylaxis or use of emicizumab.

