CRITERIA FOR EVALUATION: Efficacy: Primary efficacy endpoint: 
Change of the hFVIII activity, as measured by chromogenic substrate assay, during Weeks 49-52 post-BMN 270 infusion from baseline. Each subject's hFVIII activity during Weeks 49-52 is defined as the median of the values obtained during this 4-week window. Values for hFVIII activity will be excluded if obtained within 72 hours since the last infusion of exogenous FVIII protein concentrates. Secondary efficacy endpoints: 
Change from baseline in the annualized utilization (IU/kg/year) and infusion rate (number/year) of exogenous FVIII replacement therapy from Week 5 post-BMN 270 infusion to last visit by data cutoff (for Week 52 analysis) for subjects receiving FVIII prophylaxis during the 12 months prior to study entry, or change from baseline in the annualized utilization (mg/kg/year) of emicizumab from Week 27 post-BMN 270 infusion to last visit by data cutoff (for Week 52 analysis) for subjects receiving prior emicizumab prophylaxis.Change from baseline in the annualized number of bleeding episodes requiring exogenous FVIII replacement treatment (annualized bleeding rate, ABR) from Week 5 post-BMN 270 infusion to last visit by data cutoff (for Week 52 analysis) for subjects receiving prior FVIII prophylaxis, or from Week 27 post-BMN 270 infusion to last visit by data cutoff (for Week 52 analysis) for subjects receiving prior emicizumab prophylaxisChange from baseline in the total score of Haemo-QoL-A at Week 52 post-BMN 270 infusion		

NAME OF COMPANY BioMarin Pharmaceutical Inc. [name] [name]	SUMMARY TABLE Referring to Part of the Dossier: Volume: Page: Reference:	FOR NATIONAL AUTHORITY USE ONLY:

NAME OF FINISHED PRODUCT: BMN 270
 
NAME OF ACTIVE INGREDIENT: AAV5-hFVIII-SQ
 
Tertiary efficacy endpoints:
 
• Change from baseline in the EQ-5D-5L score at Week 52 post-BMN 270 infusion.• Change from baseline in the Work Productivity and Activity Impairment plus Classroom Impairment Questions: Hemophilia Specific (WPAI+CIQ:HS) score at Week 52 post-BMN 270 infusion.• Change from baseline in Patient Reported Outcomes, Burdens, and Experiences (PROBE) score at Week 52 post-BMN 270 infusion.		

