8 STUDY OBJECTIVES

The primary efficacy objective of the study is to:

- Assess the efficacy of BMN 270 with prophylactic corticosteroids defined as FVIII activity, as measured by chromogenic substrate assay, during Weeks 49-52 following intravenous infusion of BMN 270

The secondary efficacy objectives of the study are to:

- Assess the impact of BMN 270 with prophylactic corticosteroids on the use of exogenous FVIII replacement therapy from Week 5 to last visit by data cutoff (for Week 52 analysis) for subjects receiving prior FVIII prophylaxis or on use of emicizumab from Week 27 to last visit by data cutoff (for Week 52 analysis) for subjects receiving prior emicizumab prophylaxis
- Assess the impact of BMN 270 with prophylactic corticosteroids on the number of bleeding episodes requiring exogenous FVIII replacement therapy from Week 5 to last visit by data cutoff (for Week 52 analysis) for subjects receiving prior FVIII prophylaxis or on use of emicizumab from Week 27 to last visit by data cutoff (for Week 52 analysis) for subjects receiving prior emicizumab prophylaxis
- Assess the impact of BMN 270 with prophylactic corticosteroids on quality of life as measured by the Haemo-QoL-A questionnaire at Week 52 of the study compared to baseline

The tertiary efficacy objective of the study is to:

- Assess the impact of BMN 270 with prophylactic corticosteroids on patient-reported outcomes (PROs) (other than Haemo-QoL-A) at Week 52 of the study compared to baseline

The exploratory efficacy objective of the study is to:

- Assess the efficacy of BMN 270 with prophylactic corticosteroids defined as FVIII activity, as measured by chromogenic substrate assay, during Weeks 49-52, following intravenous infusion of BMN 270 for subjects with detectable AAV5 total antibodies below the minimum required dilution at Screening

The safety objectives of the study are to:

- Evaluate the short-term safety of BMN 270 with prophylactic corticosteroids following intravenous infusion
- Assess the long-term safety of BMN 270 with prophylactic corticosteroids

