9.4.8.1 Concomitant Hemophilia Treatments

To avoid breakthrough bleeding, subjects will only discontinue exogenous prophylactic FVIII replacement therapy 4 weeks following infusion of BMN 270 or if FVIII activity has consistently increased above 5 IU/dL, whichever is earlier. Subjects previously receiving emicizumab, given its approximate 1-month half-life, will remain on emicizumab prophylaxis until BMN 270 infusion, with their final dose administered prior to Day 1.

FVIII replacement therapy can always be taken as needed by the subject for treatment of an acute bleeding episode; the subject must carefully record his treatment and bleeding episodes in his diary. Prophylactic FVIII use can be used on a case-by-case basis and in consultation with the Medical Monitor to prevent bleeding in extenuating circumstances (eg peri-operative).

In addition, information on FVIII usage and bleeding episodes by medical history must be well-documented and available and will be collected from subjects for the 12-month period immediately preceding study enrollment. Further information on the details that should be provided as part of the subject's well-documented medical and FVIII usage history are provided in the Investigator Site File Binder.

In order to enable rigorous comparisons of pre-study versus on-study FVIII usage and bleeding episodes, the Medical Monitor will review each screened patient's prior bleed and hemophilia medication logs to determine if they are of "high-quality". Elements that will be assessed to judge the quality of such historical data may include, but are not limited to, the following:

- Date, type (eg, joint, muscle, other), location of bleeds
- Date, name, dose (calculated in IU/kg), and reason for use (eg, usual prophylaxis, one-time prophylaxis, treatment for bleed, surgery) of hemophilia medications.

9.4.8.2 Corticosteroid Treatment and/or Alternative Immunosuppressive Agent Treatment of Elevated Hepatic Transaminases

Prior to dosing, all subjects must be screened per steroid prescription guidelines to ensure the subject is eligible to receive corticosteroid treatment as outlined in the protocol. Refer to corticosteroid prescription guidelines for recommended monitoring for, and management of, potential side effects of corticosteroids, including guidance on medications that should be avoided during corticosteroid treatment.

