14.3 Secondary Efficacy Endpoints

The analyses of the secondary efficacy endpoints will be descriptive. Mean and associated 95% confidence interval will be provided for the following secondary endpoints, where the baseline value will be derived from the data in the approximately 12-month period prior to BMN 270 infusion:

- For subjects receiving FVIII prophylaxis prior to study entry, change from baseline in the annualized utilization (IU/kg/year) of exogenous FVIII replacement therapy from Week 5 post BMN 270 infusion to last visit by data cutoff (for Week 52 analysis); and separately, for subjects receiving prior emicizumab prophylaxis, change from baseline in the annualized utilization (mg/kg/year) of emicizumab from Week 27 post BMN 270 infusion to last visit by data cutoff (for Week 52 analysis)
- For subjects receiving FVIII prophylaxis prior to study entry, change from baseline in the annualized infusion rate (number/year) of exogenous FVIII replacement therapy from Week 5 post BMN 270 infusion to last visit by data cutoff (for Week 52 analysis); and separately for subjects receiving prior emicizumab prophylaxis, change from baseline in the annualized utilization (mg/kg/year) of emicizumab from Week 27 post BMN 270 to last visit by data cutoff (for Week 52 analysis) infusion
- Change from baseline in the annualized number of bleeding episodes (number/year) requiring exogenous FVIII replacement treatment from Week 5 post-BMN 270 infusion to last visit by data cutoff (for Week 52 analysis) for subjects receiving prior FVIII prophylaxis, or from Week 27 post-BMN 270 infusion to last visit by data cutoff (for Week 52 analysis) for subjects receiving prior emicizumab prophylaxis from baseline

Mean change from baseline and associated 95% confidence interval will be calculated for the total score of Haemo-QoL-A at Week 52 post-BMN 270 infusion as well.

The missing value of the change for annualized utilization and annualized infusion rate will be imputed as 0. The missing value of the change for annualized number of bleeding episodes will be imputed using the median value of the changes of all observed cases.

A sensitivity analysis is planned to analyze ABR using a generalized linear mixed model assuming negative binomial as the underlying distribution. The model will include period (pre- to post-BMN 270 infusion) as the only factor, repeated within subject. The actual

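### For subjects previously on emicizumab, the protocol defines the secondary use endpoint inconsistently, and the Section 14.3 version cannot register FVIII use after infusion

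*Protocol*

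**What the plan says.** All references are to the current (Amendment 2) text.

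- **Section 9.7.3.1** gives the use variable for prior-emicizumab subjects as "change in administration of exogenous FVIII replacement therapy from Week 27 post-BMN 270 infusion to last visit by data cutoff". It states no unit and no annualization for them.
- **Synopsis, Criteria for Evaluation** gives "change from baseline in the annualized utilization (mg/kg/year) of emicizumab from Week 27 post-BMN 270 infusion to last visit by data cutoff".
- **Section 14.3, utilization bullet**, and the matching bullet in the synopsis Statistical Methods, give "and separately, for subjects receiving prior emicizumab prophylaxis, change from baseline in the annualized utilization (mg/kg/year) of emicizumab from Week 27".
- **Section 14.3, infusion-rate bullet**, and its synopsis counterpart, open for prior-FVIII subjects with "change from baseline in the annualized infusion rate (number/year) of exogenous FVIII replacement therapy". For prior-emicizumab subjects they then return to emicizumab in mg/kg/year.
- **Section 8 and the synopsis Objectives** put the same clause, "or on use of emicizumab from Week 27 to last visit by data cutoff (for Week 52 analysis) for subjects receiving prior emicizumab prophylaxis", in both the use objective and the bleeding objective.
- **Section 9.4.8.1** keeps these subjects on emicizumab until infusion, "with their final dose administered prior to Day 1". The same section lets every subject take FVIII as needed for an acute bleed and allows prophylactic FVIII case by case. Section 9.7.3.1 adds that, for recurrent bleeding, a return to FVIII prophylaxis or to emicizumab may be discussed.

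**The concern.** A named secondary endpoint should have one definition. Here two sections name different drugs in different units for the same subjects, so analysts following Section 9.7.3.1 and Section 14.3 would produce different tables. The trial is open label and informal analyses are allowed along the way (Section 14.1.1). Leaving the choice open therefore lets it be made after the data are seen.

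The Section 14.3 version also has a weakness of content. It tracks a drug that the protocol itself stops before infusion, while the drug permitted for bleeds afterwards is FVIII. A prior-emicizumab subject who responds poorly and is managed with FVIII would show the same favourable change as one who needs no treatment.

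**Working it through.** No figure in the protocol needs reproducing. The check sets the statements side by side and then follows each definition through.

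**Step 1. Use measure for prior-emicizumab subjects, by place.**

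| Place | Drug measured from Week 27 | Unit |
|---|---|---|
| Synopsis, Objectives | emicizumab | none given |
| Synopsis, Criteria for Evaluation | emicizumab | mg/kg/year |
| Synopsis, Statistical Methods | emicizumab | mg/kg/year, in both use bullets |
| Section 8 | emicizumab | none given |
| Section 9.7.3.1 | FVIII | none given |
| Section 14.3 | emicizumab | mg/kg/year, in both use bullets |

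Five places name emicizumab and one names FVIII.

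**Step 2. Infusion-rate bullet.** For prior-FVIII subjects the utilization bullet is in IU/kg/year and the infusion-rate bullet in number/year. For prior-emicizumab subjects both bullets are in mg/kg/year. The second duplicates the first, and a count of administrations is defined nowhere for this group.

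**Step 3. Bleeding objective against its endpoint.** In Section 8 and the synopsis Objectives, the bleeding objective turns to emicizumab use for this group. The corresponding endpoint (synopsis Criteria for Evaluation, Section 9.7.3.1, Section 14.3) counts FVIII-treated bleeds from Week 27. Objective and endpoint do not match.

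**Step 4. What each definition returns.** Let E be a subject's baseline emicizumab use (mg/kg/year). Let F0 and F1 be annualized FVIII use (IU/kg/year) at baseline and from Week 27. Suppose emicizumab is not resumed.

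- Section 14.3: change = 0 − E = −E, whatever F1 is.
- Section 9.7.3.1, taken as annualized IU/kg/year (an assumption, since it gives no unit): change = F1 − F0.

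The protocol gives no values for E, F0 or F1. The values below are assumed, to show the range of behaviour.

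| F0 | F1 | Section 14.3, E = 50 | Section 14.3, E = 100 | Section 9.7.3.1 |
|---|---|---|---|---|
| 0 | 0 | −50 | −100 | 0 − 0 = 0 |
| 100 | 0 | −50 | −100 | 0 − 100 = −100 |
| 0 | 500 | −50 | −100 | 500 − 0 = +500 |
| 100 | 2,000 | −50 | −100 | 2,000 − 100 = +1,900 |

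The Section 14.3 columns do not move with F1. The Section 9.7.3.1 column does, and in the last two rows it has the opposite sign.

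**Step 5. What still captures FVIII use under Section 14.3.** Bleeds treated with FVIII enter the annualized bleeding rate for this group from Week 27. The amount of FVIII and the number of infusions, including any given prophylactically, enter no analysis listed there for these subjects.

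**The case against.** The strongest reply has four parts.

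*Emicizumab use can vary after Week 27.* Section 9.7.3.1 allows its resumption to be discussed, so the measure can show failure by that route. This stands. The change is −E only when emicizumab is not resumed.

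*The prior-FVIII group also stops prophylaxis by protocol, at 4 weeks or earlier, and nobody calls its endpoint empty.* In part this stands: both measures show whether subjects stay off their previous prophylaxis. The groups still differ. For prior-FVIII subjects the drug measured is also the one used for bleeds and for resumed prophylaxis, so treatment failure shows in the measure. For prior-emicizumab subjects, failure managed with FVIII does not.

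*Five of six places agree, so Section 9.7.3.1 is a simple slip.* That may be so. Correcting it alone would remove the conflict over the drug, but it would leave the duplicated bullet and the mismatched objective. It would also delete the only definition that records this group's FVIII amount.

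*The analyses are descriptive and the subgroup may be very small.* This stands, and it limits the weight of the point.

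A reader might also infer that FVIII use in this group can only stay flat or rise. The documents do not support that. The synopsis Study Rationale says that patients on emicizumab still need episodic FVIII for breakthrough bleeds, so baseline use can exceed zero and fall.

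**Conclusion.** The inconsistency is confirmed in the current text: two different drugs for one endpoint, a duplicated mg/kg/year measure where a number per year belongs, and a bleeding objective that does not match its endpoint. Under Section 14.3 the change is minus baseline unless emicizumab is resumed, and a subject managed with FVIII is missed.

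Two stronger readings should be resisted. One is that every such subject scores a 100% reduction. Section 14.3 defines a mean absolute change and no percentage, and resumption is possible. The other is that FVIII use disappears from the analysis altogether. Treated bleeds remain in the annualized bleeding rate, and Section 9.7.3.1 still names FVIII administration. What Section 14.3 omits is amount and infusion count.

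The whole use result for this group depends on which section is followed. The group is an unstated subset of approximately 20 subjects. All secondary analyses are descriptive, so the primary test, its significance level and the sample size are untouched. The point should be corrected before the Week 52 analysis, but it does not threaten the trial's main conclusion. The conclusion rests on the text itself. The assumed values in the working only illustrate that the two definitions can diverge in sign.

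**What to change.** Reconcile the six statements: synopsis Objectives, synopsis Criteria for Evaluation, synopsis Statistical Methods, Section 8, Section 9.7.3.1 and Section 14.3.

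1. For prior-emicizumab subjects from Week 27, report change in FVIII IU/kg/year and FVIII infusions/year alongside change in emicizumab mg/kg/year.
2. In the infusion-rate bullet (Section 14.3 and synopsis Statistical Methods), replace the repeated mg/kg/year text for this group with a number/year measure.
3. In Section 8 and the synopsis Objectives, restate the bleeding objective for this group as bleeding episodes from Week 27.

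The cost is wording in six places and a few descriptive rows. No new data are needed: 12 months of therapy history is an entry requirement (Section 9.3.1), the historical logs are reviewed for drug name, dose and reason (Section 9.4.8.1), and factor use is asked at each visit (Section 9.7.3.1). Nothing in the treatment of subjects changes.

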
FVIII interventional studies). The consequence of multiple bleeding events is the development of debilitating multiple-joint arthropathy and substantially increased risk of death. Chemical modification (eg, direct conjugation of polyethylene glycol (PEG) polymers) and bioengineering of FVIII (eg, FVIII-Fc fusion proteins) improve half-life by approximately 50%, and thus, show promise in reduced dosing and maintaining activity levels above a 1% trough for a greater proportion of the dosing interval. However, patients with severe HA who are treated with extended half-life FVIII remain dependent on multiple infusions to maintain critical levels of FVIII activity. While emicizumab prophylaxis has yielded lower bleed rates compared to prior FVIII prophylaxis, it does not physiologically recapitulate the coagulation system, requires chronic, life-long therapy, and still necessitates the use of episodic FVIII concentrates for treatment of breakthrough bleeds. There is therefore a strong unmet need for a fully preventive treatment of HA to give patients a FVIII level compatible with a normal and hemorrhage-free life.
 
Gene therapy offers the potential of disease-modifying therapy by continuous endogenous production of active FVIII following a single intravenous infusion of a vector encoding the appropriate gene sequence for long-term episomal expression. HA is well-suited for a gene replacement approach because clinical manifestations are attributable to the lack of a single gene product (FVIII) that circulates in minute amounts (200 ng/ml) in the plasma. Tightly regulated control of gene expression is not essential, and even modest increases in the level of FVIII (any increase of the plasma level by 2 ng/ml induces an increase in activity of 1%) can ameliorate the severe form of hemophilia A. Thus, relatively small changes in endogenous FVIII activity can result in clinically relevant improvements in disease phenotype. Finally, the circulating FVIII response to gene transduction can be assessed using validated quantitative rather than qualitative endpoints that are easily assayed using established laboratory techniques.
 
Several different gene transfer strategies for FVIII replacement have been evaluated, but adeno-associated viral (AAV) vectors show the greatest promise. They have an excellent and well-defined safety profile, and can direct long-term transgene expression with tropism and promoter specificity for specific tissues, such as the liver (for serotypes 2, 5 and 8 among others). Indeed, an ongoing gene therapy clinical trial for a related disorder, hemophilia B, has established that stable (median follow-up of 6.7 years) expression of human factor IX (hFIX) at levels that are sufficient for conversion of their bleeding phenotype from severe to moderate or mild is achievable following a single peripheral vein infusion of AAV8-hFIX vector. Several participants in this trial have been able to discontinue factor prophylaxis without suffering spontaneous hemorrhages, even when they undertook activities that previously resulted in bleeding. Thus, gene therapy treatment has resulted in a substantial improvement in their quality of life.
 
BMN 270 is an AAV5-based gene therapy vector that expresses the SQ form of hFVIII under the control of a hybrid human liver-specific promoter (Figure 1).
		

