14.8 Determination of Sample Size

Approximately 20 subjects may be dosed in the study, including at least 16 subjects who are AAV5 antibody-negative and up to 25% of the total number of subjects with an AAV5 antibody titer that is detectable but below the minimum required dilution (< 20) at Screening. For the primary endpoint, a sample size of 16 will provide 85% power to demonstrate that

the change in hFVIII activity during Weeks 49-52 from baseline is greater than 0, assuming an effect size of 0.8, using a one-sample t-test at the 1-sided significance level of 0.025 (or equivalently, at the 2-sided significance level of 0.05). The effect size of 0.8 is assumed conservatively based on the results from 270-201 and the interim results from 270-301.

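### The use endpoints for prior-FVIII subjects count only FVIII, so a treatment failure moved to emicizumab is scored as a large reduction in use

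*Protocol*

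**What the plan says.** All references are to the current protocol text (Amendment 2).

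- **Use endpoints, Section 14.3.** The analysis is "For subjects receiving FVIII prophylaxis prior to study entry, change from baseline in the annualized utilization (IU/kg/year) of exogenous FVIII replacement therapy", with a parallel bullet for the infusion rate, from Week 5 to the last visit by data cutoff. Emicizumab is measured only in the other group: "and separately, for subjects receiving prior emicizumab prophylaxis, change from baseline in the annualized utilization (mg/kg/year) of emicizumab", from Week 27.
- **Bleeding endpoint, Section 9.7.3.1.** "Change in the annualized number of bleeding episodes requiring exogenous FVIII replacement treatment (annualized bleeding rate, ABR) from Week 5 post-BMN 270 infusion", or from Week 27 for prior-emicizumab subjects. Time on resumed or new prophylaxis is neither excluded nor reported separately.
- **Prophylaxis after infusion.** For recurrent bleeding, Section 9.7.3.1 says the Investigator and Medical Monitor "will discuss whether to resume prior FVIII prophylaxis or use of emicizumab". The Synopsis and Section 9.1 name only resumption of earlier FVIII prophylaxis.
- **Prohibited drugs, Section 9.4.8.** Other investigational therapy, fitusiran, concizumab and efavirenz are listed; emicizumab is not. The Investigator may add medication for prophylactic care if it is not prohibited.
- **Emicizumab and bleeding, Synopsis.** "While emicizumab prophylaxis has yielded lower bleed rates compared to prior FVIII prophylaxis", although FVIII is still needed for breakthrough bleeds.
- **Imputation and sensitivity, Section 14.3.** A missing change in use is set to 0, and a missing change in ABR to the median of the observed changes. The sensitivity analyses cover missing data and a negative binomial model with period as its only factor. None deals with a change of product.

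**The concern.** Which product is counted depends on what the subject took before entry, but the prophylaxis he may take after infusion is not tied to that product. Two prior-FVIII subjects can fail equally and be scored very differently: FVIII resumed counts against BMN 270, while emicizumab started shows up as FVIII saved. Under Section 14.3 the same gap runs in reverse for a prior-emicizumab subject placed on FVIII prophylaxis, whose measured emicizumab use stays low.

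The study has one arm and compares each subject with his own past, so nothing offsets the error. For use, it always favours BMN 270. At stake are the mean and 95% confidence interval for the reduction in use. The reading of ABR is affected to a lesser extent.

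**Working it through.** **The plan's own figure.** The document gives no figure for the use or bleeding endpoints. Its only sample-size statement concerns the primary endpoint: "a sample size of 16 will provide 85% power to demonstrate that" an effect exists, "assuming an effect size of 0.8, using a one-sample t-test at the 1-sided significance level of 0.025". With 15 degrees of freedom and noncentrality 0.8 × √16 = 3.2, the exact power is 84.8%, so the stated 85% reproduces. This point does not affect it.

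**Inputs from the Synopsis.** FVIII prophylaxis 2–3 times a week gives 104–156 infusions a year (midpoint 130). Median ABR is 1–4 on prophylaxis and 4.5–18 on on-demand treatment in the retrospective study.

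**Assumptions.** A window of 48 weeks (Weeks 5–52); switch at Week 5, 12, 26 or 39; before the switch, 8 treated bleeds a year × 2 infusions = 16, or 18 × 3 = 54 infusions a year; no FVIII after a switch to emicizumab.

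**Use in one failing subject.** Let b be baseline use, p the pre-switch FVIII rate and w the weeks from Week 5 to the switch.

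- Scored change after a move to emicizumab: p·w/48 − b
- Scored change after resuming FVIII at rate b: [p·w + b·(48 − w)]/48 − b

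At Week 26, w = 21. With b = 130 and p = 16:

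- emicizumab: 16 × 21/48 − 130 = −123.0
- FVIII resumed: (16 × 21 + 130 × 27)/48 − 130 = −49.9

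| Switch week (b = 130) | Moved to emicizumab (p = 16; p = 54) | Resumed FVIII (p = 16; p = 54) |
|---|---|---|
| 5 | −130; −130 (100%) | 0; 0 |
| 12 | −127.7 (98%); −122.1 (94%) | −16.6; −11.1 |
| 26 | −123.0 (95%); −106.4 (82%) | −49.9; −33.2 |
| 39 | −118.7 (91%); −91.8 (71%) | −80.8; −53.8 |

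Over baselines of 104–156, the scored reduction after a move to emicizumab runs from 63% to 100%. It is 100% only if no FVIII is used from Week 5 on.

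**Effect on the mean.** The gap between the two scores is b·f, where f is the fraction of the window spent on the uncounted product. One switcher therefore moves the mean of n subjects by b·f/n. The percentages below assume that his baseline equals the group mean.

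- f = 1, n = 16: 1/16 = 6.3%, or 130/16 = 8.1 infusions a year (6.5–9.75 for baselines of 104–156). Two switchers: 12.5%.
- f = 1, n = 10: 10%, or 13.0 infusions a year (10.4–15.6).
- Switch at Week 26, f = 27/48 = 0.5625: 3.5% if n = 16, 5.6% if n = 10.

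**ABR.** With pre-switch rate r, post-switch rate e and window T weeks, ABR = [r·w + e·(T − w)]/T. The grid took baselines of 1, 2 and 4; r of 4.5, 8 and 18; e of zero or half of baseline; switch at Week 9, 16 or 26; and T of 48 or 100 weeks.

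- Baseline 4, r = 8, e = 2, switch at Week 16 (w = 11), T = 48: (88 + 74)/48 = 3.38, a change of −0.62. Without the switch: +4.
- Baseline 1, r = 8, e = 0.5, switch at Week 26 (w = 21), T = 48: (168 + 13.5)/48 = 3.78, a change of +2.78. Without the switch: +7.

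ABR is below its no-switch value in all 108 scenarios, but below baseline in only 65.

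**The case against.** **The sentence in Section 9.7.3.1 is ambiguous.** The verb for resuming may govern both products, so that each subject returns to his own earlier one; the endpoint would then match. The ambiguity is real. But Section 9.4.8 leaves emicizumab open to any subject on either reading, so the scoring gap remains.

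**The SAP may hold a rule for a change of product.** It may; it is not shown. The protocol, however, itself fixes which product counts for which subject, and that definition creates the asymmetry.

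**Observed outcomes regardless of later therapy are a legitimate target.** This stands for bleeding, and is why ABR should stay as recorded. It does not rescue the use endpoints, because use regardless of later therapy would have to include both products.

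**A reader might infer that a failure is recorded as success on every use and bleeding endpoint.** The documents do not support that. Zero use is an upper bound. The bleeds that prompt a switch count in the ABR, which stays at or above baseline in 43 of the 108 scenarios. Resumed FVIII also protects time in the ABR window, so that effect is not peculiar to emicizumab.

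**The consequence is limited.** This stands. The secondary analyses are descriptive, and loss of expression is assessed separately through FVIII activity at Weeks 49–52.

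**Conclusion.** The point holds for the use endpoints: as defined, they credit BMN 270 with FVIII that emicizumab has replaced. Under the stated assumptions one switcher is scored with a 63–100% reduction, and he overstates the mean reduction by up to 1/n of mean baseline use. The value of n is not stated. Sixteen is the minimum number of AAV5-antibody-negative subjects, not the number who entered on FVIII, so 6.3% is one case and 10% at n = 10 another. Whether anyone will switch is unknown. Switch weeks, bleed counts, infusions per bleed and post-switch bleeding are illustrative; they change the size but not the direction.

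For ABR only the weaker statement holds: lower than without the switch, not necessarily lower than baseline. The analysis runs to the data cutoff, after every subject has reached Week 52, so early enrollees may contribute more post-switch time than 48 weeks allows. How much more cannot be said, because the length of accrual is not given.

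The definition should be corrected, but no hypothesis test depends on it.

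**What to change.** In Section 14.3:

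1. For time on routine prophylaxis with the product not counted for that subject, score use as no reduction from baseline (change 0). This matches the plan's own rule for a missing change in use. Keep observed use when the counted product is resumed, since it already counts. In the Week 26 example the switcher would then score −33.2 to −49.9, the same as the subject who resumes FVIII.
2. Report as-recorded use alongside, with the number of subjects on any routine prophylaxis, FVIII or emicizumab, at the cutoff.
3. Keep ABR as recorded. Add a sensitivity analysis limited to time before any routine prophylaxis is started or resumed after the Week 5 or Week 27 start of the window. Do not substitute baseline ABR: it was measured on prophylaxis, is not the plan's rule for missing ABR, and could hide worse observed bleeding.

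Two conflicts must be reconciled; this review takes no view on the clinical content. Section 9.7.3.1 differs from the Synopsis and Section 9.1 on which prophylaxis may be resumed or started. For prior-emicizumab subjects, Section 9.7.3.1 measures exogenous FVIII, while the Synopsis and Section 14.3 measure emicizumab.

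The cost is revised wording and one derived variable. Sections 9.4.8, 12.5 and 12.6 already collect concomitant medication and hemophilia therapy. The downside is a smaller reported reduction if anyone switches.
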